## LIST OF ACRONYMS, ABBREVIATIONS, AND DEFINITIONS OF TERMS

ABC-FX	Aberrant Behavior Checklist – Community Edition – Factored for FXS
AE	Adverse Event
AKT	serine/threonine-specific protein kinase (also PKB – protein kinase B)
APP	Amyloid Precursor Protein
CBC	Complete blood count
CCC	Clinical Coordination Center
CDE	Common Data Elements
CFR	Code of Federal Regulations
CGI-I	Clinical Global Impression – Improvement
CGI-S	Clinical Global Impression - Severity
CIRB	Central Institutional Review Board
CMP	Comprehensive metabolic profile
CRF	Case report form
CS	Clinically Significant
CSS PI	Clinical Study Site PI
DCC	Data Coordination Center
DM	Data Management
DSMB	Data Safety Monitoring Board
DQ	Developmental quotient
eCRF	Electronic Case Report Form
EDC	Electronic data capture
EKG	Electrocardiogram
ELC	Early Learning Composite
ERK	Extracellular signal-related kinase
ERP	Event related potentials
FDA	Food and Drug Administration
FMR1	Fragile X Mental Retardation-1 gene
FMRP	Fragile X Mental Retardation Protein
FXS	Fragile X syndrome
GCP	Good Clinical Practice
HBsAg	Hepatitis B surface antigen
HIV	Human Immunodeficiency Virus
HIPAA	Health Insurance Portability and Accountability Act
ICH	International Conference on Harmonization
IMM	Independent Medical Monitor
mGluR5	Metabotropic Glutamate Receptor – Type 5
MedDRA	Medical Dictionary for Regulatory Activities
MMP9	Matrix Metalloprotein 9
MSEL	Mullen Scales of Early Learning
MTD	Maximum tolerated dose
NINDS	National Institute of Neurological Disorders and Stroke
PK	Pharmacokinetics
PLS-5	Preschool Language Scale Version 5
PPI	Protocol Principal Investigator
PSC	Protocol Steering Committee
SAE	Serious adverse event
SOA	Schedule of Activities
TSH	Thyroid stimulating hormone
VAS	Visual analog scale
VABS	Vineland Adaptive Behavior Scale

AFQ056 for Language Learning in Children with FXS

Version v15

Version date 02/03/2021

## **SYNOPSIS**

**Study Title: Effects of AFQ056 on Language Learning in Young Children with Fragile X Syndrome (FXS)**

**Short Title: AFQ056 for Language Learning in Children with FXS**

### **Objectives**

The overall goals are to change the paradigm for development of mechanism targeted pharmacotherapy in neurodevelopmental disorders and provide a definitive test of the mGluR theory in humans by determining whether AFQ056, an mGluR5 negative modulator, can enhance neural plasticity in the form of language learning during an intensive language intervention in very young children with fragile X syndrome. This trial therefore will use an innovative but exploratory new trial design to develop a different way to examine efficacy of an agent with substantial support as a drug targeting CNS plasticity in preclinical models of a developmental disorder. If the design is successful, this trial can serve as a model for future trials of mechanistically-targeted treatments operating on neural plasticity in other neurodevelopmental disorders.

**Primary objective:** To demonstrate greater improvement in language in young children with FXS treated with AFQ056, using an overall weighted communication score, in combination with an intensive standardized parent-implemented language learning intervention, relative to those treated with the language learning intervention and placebo, after 6 months of intervention, as a marker of drug effect on neural plasticity, the core problem in the disorder.

**Key Secondary Objective:** To show greater improvement in specific language, cognitive, and adaptive measures in the combination AFQ056/language intervention group relative to the language intervention/placebo group.

**Other Secondary and Exploratory Objectives:** (1) To show improvement in specific measures from ERP and eye tracking biomarkers in the combination AFQ056/language intervention group relative to the language intervention/placebo group. (2) Examine long-term safety and tolerability of AFQ056 in young children with FXS; (3) To explore whether greater improvement occurs in additional language, cognitive, adaptive and behavioral measures in the combination AFQ056/language intervention group relative to the language intervention/placebo group; (4) To explore improvement in multiple additional measures from the ERP and eye tracking in the combination AFQ056/language intervention group relative to the language intervention/placebo group; (5) To explore whether the normalization of eye tracking/pupillometry biomarkers is correlated with improvement in clinical outcome markers including language; (6) To explore whether normalization of blood biomarkers of translational pathways regulated by FMRP and mGluR5 receptors is associated with language, functional and/or biomarker improvements from AFQ056 treatment; (7) To examine if blood levels of AFQ056 correlate with improvement in language, functional or biomarker measures, (8) To examine if longitudinal analysis shows an improvement in the rate of change of language, functional or biomarker responses with the language intervention alone, and further improvement in rate of change when AFQ056 is added to the language intervention

### **Design and Outcomes**

**Trial Design:** The trial will be a phase II double blind placebo-controlled parallel-group flexible-dose forced-titration study that will use a novel design to address the impact of AFQ056 on language learning in 3-6 year old children with FXS. The flexible dose design will mimic practice,

AFQ056 for Language Learning in Children with FXS

Version v15

Version date 02/03/2021

take into account differential responsiveness and the known inter-child variability in drug levels with AFQ056, and allow use of the maximum tolerated dose (MTD) where MTD is defined as the maximum tolerated dose of the available dose levels in the protocol, which is felt likely to be most effective. There will be a 4-month single-blind placebo lead in after screening assessments during which subjects will have therapy treatments as usual to control for the effects of the language intervention. The placebo lead-in will also control for placebo effects which are prominent in clinical trials in FXS. This will be followed by an 8-month placebo-controlled phase in which 100 subjects with FXS will have AFQ056 baseline assessments and be randomized 1:1 to AFQ056 or placebo. Dose titration to MTD starting at 25 mg AFQ056/matching placebo will occur over 2 months and then subjects will have language intervention baseline assessments and initiate the language intervention, remaining on a stable AFQ056/placebo dose for the next 6 months. After 8 months of treatment in the placebo-controlled phase (6 months of language intervention), all subjects will have final assessments and will enter the open label extension and be treated with active drug according to the same schedule as in the placebo-controlled phase with 2 months of flexible dose titration to the MTD followed by a period of stable treatment. The duration of the stable treatment will depend on when the subject was enrolled into the study; those enrolled prior to June 15-30, 2019 will receive a 6-month period of stable treatment, and the open label extension may be shortened on a sliding scale for those enrolled after June 15, 2019, such that their treatment including weaning, if necessary, will end before August 31, 2021, with the exact length of the stable treatment period in the extension being determined by how long after June 15 they enroll and what dose of drug they are receiving in the open label treatment period (higher doses will have a longer weaning period of maximally 2 weeks for those on 75-100 mg BID, but 1 week for 50 mg BID, and no weaning period for lower doses). The total duration of the stable treatment for those enrolled after June 15, 2019 will range from 6 months to no open label extension, depending on the number of months after June 15, 2019 the subject is enrolled into the study. As such, some subjects will have an acute dose decrease if they were on a dose of 50-100 mg BID of active drug in the initial phase but experience from the Pediatric PK study conducted previously suggests that children can stop AFQ056 without withdrawal symptoms and the dose decrease and titration in the open label extension are unavoidable to maintain the blind of the study through the completion of the placebo-controlled period by the final participant. The open-label extension will allow all children a period of active drug exposure to make recruitment feasible, despite the long placebo period, and will allow additional collection of long-term safety data. Subjects will continue the language intervention through the extension phase to gain additional data on long-term effects of the combination of AFQ056 and the language intervention on developmental trajectory and the ERP biomarker.

#### Interventions and Duration

**AFQ056:** AFQ056 is a highly selective mGluR5 negative allosteric modulator shown to be effective in reversing dendritic spine and behavioral phenotypes in the mouse model of FXS. It is administered orally as a suspension at a concentration of mg/ml. Dosing range is expected to be 25-100 mg BID.

**Language Intervention:** The language intervention, which was developed by [name] and colleagues, showed benefit for language development over 6 months (the period assessed in the placebo-controlled phase of this trial) in a pilot study of young children with FXS, can be taught to families with standardized delivery across sites, and implemented in the home through video-conferencing with families.

**Time of Study Participation:** Subjects will be in the study a total of 21 months (Screening and placebo run-in 4 months prior to randomization, 8 months placebo-controlled treatment, 8 months open-label extension, 1 month follow up after final assessment visit/visit 14).

**\*\*Note:** Due to study drug expiration, the duration of the open label extension may be shortened on a sliding scale for those enrolled after June 15, 2019, such that their treatment including weaning, if necessary, will end before August 31, 2021, with the exact length of the stable treatment period in the extension being determined by how long after June 15 they enroll and what dose of drug they are receiving in the open label treatment period. The total duration of the stable treatment for those enrolled after June 15, 2019 will range from 6 months to no open label extension, depending on the number of months after June 15, 2019 the subject is enrolled into the study.

**Duration of Enrollment:** It is expected enrollment will occur over 18 months. Enrollment must end at the end of February 2020 due to study drug expiration at the end of August 2021.

**Schedule and Type of Evaluations:** The Language primary outcome assessment (weighted communication scale, WCS) will be obtained at screening, randomization (AFQ baseline), 2 (language intervention baseline), 4, 6, 8, 10, 12, 16 months and post-intervention follow up at 17 months. Cognition, language and behavioral assessments including the, MacArthur Bates Communicative Development Inventory, Preschool Language Scale – 5th Edition (PLS-5), Visual Analog Scale (VAS) of language, Clinician Global Impression-Improvement and Severity (CGI-I, CGI-S) for language and overall function, Mullen Scales of Early Learning (MSEL) Composite and Subscales, Vineland Adaptive Behavior Scale-Version 3 (Vineland-3); Aberrant Behavior Checklist-fragile X validated version (ABC-FX), and a VAS of behavior will be performed regularly throughout the protocol according to the Schedule of Assessments (below, Section 6.1, Table 7) ; Biomarkers including ERP, eye tracking/pupillometry, and blood biomarkers (ERK, AKT, S6 kinase, APP, MMP9, RNA, FMRP, DNA) will also be obtained throughout the protocol according to the Schedule of Assessments. Safety measures will include CBC, CMP, TSH, EKG, adverse events, suicidality.

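### The June 2019 and February 2020 cut-offs do not follow from the stated August 2021 drug expiry, and the protocol gives conflicting rules for the length of the open-label extension

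*Combined protocol and SAP*

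**What the plan says.** **Timetable.** The Synopsis (Interventions and Duration) sets the course as "Screening and placebo run-in 4 months prior to randomization, 8 months placebo-controlled treatment, 8 months open-label extension", then one month of follow-up. On weaning, the Synopsis (Design and Outcomes) says "higher doses will have a longer weaning period of maximally 2 weeks for those on 75-100 mg BID", with one week at 50 mg BID and none below that. Section 2.1, footnote 16 of Table 7 (Section 6.1) and Section 9.1 count from consent.

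**Limit.** Treatment is arranged "such that their treatment including weaning, if necessary, will end before August 31, 2021".

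**Cut-offs.** The Synopsis says "those enrolled prior to June 15-30, 2019 will receive a 6-month period of stable treatment" and "The total duration of the stable treatment for those enrolled after June 15, 2019 will range from 6 months to no open label extension". Enrolment closes in February 2020, and the only reason given is expiry: "Enrollment must end at the end of February 2020 due to study drug expiration at the end of August 2021".

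**How binding the shortening is.** The passages differ:
- The Synopsis and Section 2.1 say the extension *may* be shortened for later enrollees, to the extent needed to finish before the August limit.
- Section 3 says in its opening paragraph that the extension *will* be shorter for those enrolled after 15 June 2019. It later makes the stable period depend on the time from that date to enrolment and on dose.
- Footnote 16 makes the length depend on consent date and dose. For shortened extensions it keeps visits at their usual months, with an early termination visit by 31 August 2021.

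**The concern.** The protocol attributes the cut-offs to drug expiry, so they should follow from the expiry date and the phase lengths. They do not. They fall about six months earlier than an August 2021 expiry requires.

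This leaves sites with two ways to set a child's extension: count forward from 15 June 2019, or count back from 31 August 2021. For the same child these can give very different lengths of open-label treatment. Long-term safety, for up to 16 months, is the first purpose that Section 2.1 lists for the extension, and Section 1.3.1 states a hypothesis over that period. The conflict also has a safety side. If the cut-offs are right and the August date is wrong, the stated end date would run past expiry.

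**Working it through.** **Inputs.** Expiry 31 August 2021. Consent to month 16: 4 + 8 + 8 = 20 months. Consent to month 8: 4 + 8 = 12 months. Wean: 0, 7 or 14 days.

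**1. Try to reproduce the stated cut-offs.**
- Latest consent for a full extension = expiry − wean − 20 months.
- Latest consent before the extension falls to nothing = expiry − 12 months (no wean).

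| Expiry assumed | Full extension, 14-day wean | 7-day wean | No wean | Extension falls to nothing |
|---|---|---|---|---|
| 31 Aug 2021 (stated) | 17 Dec 2019 | 24 Dec 2019 | 31 Dec 2019 | 31 Aug 2020 |
| 28 Feb 2021 (trial value) | 14 Jun 2019 | 21 Jun 2019 | 28 Jun 2019 | 28 Feb 2020 |
| Protocol's cut-offs | 15–30 Jun 2019 | | | end Feb 2020 |

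The stated expiry reproduces neither cut-off. An expiry six months earlier comes close to both.

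**2. Run the protocol's dates forward.**
- Consent 15 June 2019: month 16 is 15 February 2021. A 14-day wean ends on 1 March 2021, 183 days before 31 August 2021.
- Consent 15 December 2019: month 16 is 15 August 2021. A 14-day wean ends on 29 August 2021, so the full course fits.
- Consent 29 February 2020: month 8 is 28 February 2021, leaving 184 days. After 2 months of titration (to 28 April), a 14-day wean leaves 28 April to 17 August = 111 days, or 111 / 30.4375 = 3.6 months of stable treatment. With no wean it is 125 / 30.4375 = 4.1 months.

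For a child on schedule and enrolled by the deadline, an August 2021 expiry therefore never produces the bottom of the range.

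**3. Other readings.**
- The 5-day visit window (Section 6.2) moves the full-extension cut-off only to 12–26 December 2019.
- Counting the follow-up month as drug time (21 months) moves it only to 30 November 2019.
- Reading enrolled as randomised widens the gap: 15 June 2019 + 16 months + 14 days = 29 October 2020.

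**4. Size of the disagreement.** The documents do not spell out the scale. As an illustration, assume the 8-month extension loses one month for each month after 15 June 2019. It then reaches zero at 15 February 2020, close to the stated deadline.

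| Consent | Counting from 15 June 2019 | Counting back from 31 Aug 2021 | Difference |
|---|---|---|---|
| 15 Sep 2019 | 8 − 3 = 5 months | 8 months | 3 months |
| 15 Dec 2019 | 8 − 6 = 2 months | 8 months | 6 months |
| 29 Feb 2020 | 0 | about 6 months (184 days) | about 6 months |

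**5. Who is affected at the version date (02/03/2021, read as 3 February 2021).** Month 8 is consent + 12 months, so on-schedule children consented up to early February 2020 have entered the extension. Those consented later that month are still in the blinded phase and about to enter. A child consented on 15 June 2019 is 12 days from month 16.

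**The case against.** The strongest reply is that the operative rule is tied to 31 August 2021. The Synopsis and Section 2.1 say only that the extension may be shortened, and only so far as that date requires. Footnote 16 tells sites to keep the usual visits and terminate by that date. Applied literally, this shortens nobody consented before about mid-December 2019 and gives an end-February 2020 child about 6 months. A floor that nobody reaches would then be loose wording.

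This stands as a reading of those passages. A reader might infer that children are losing six months of extension without need; the documents do not show that, because a site following the conditional wording would not cut those extensions. The reply does not remove the conflict, since Section 3 is unconditional and makes the stable period depend on time since 15 June 2019.

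A second reply is that closing enrolment in February 2020 is compatible with an August 2021 expiry: 4 + 8 + 6 = 18 months gives the last child a 6-month extension. This also stands, and the close had passed before this version. What remains is that the text says enrolment *must* close because of expiry, and the stated expiry does not force it.

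Third, the 16-month safety aim is worded as a maximum, and earlier enrollees can still supply such data. That is correct, so the aim is not lost. The amount of exposure is what is uncertain.

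**Conclusion.** The protocol contradicts itself on how long the extension lasts. The 15 June 2019 cut-off, the no-extension floor and the stated reason for the February 2020 close do not follow from expiry at the end of August 2021. The conditional and unconditional wordings give different lengths for children consented after mid-June 2019, by up to about 6 months per child. The number of such children is not given, so total exposure at stake cannot be estimated.

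The date arithmetic assumes on-schedule visits, a clock that starts at consent and a wean of at most 2 weeks. The size also depends on how sites apply the scale.

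A reader might infer that the cut-offs were carried over from a February 2021 expiry, or that August 2021 is the correct date. The documents state neither. They show only that the dates disagree, and which one is right should not be presumed. The month 0 to 8 primary comparison is unaffected.

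**What to change.** - Confirm the drug expiry date and state it once.
- Reconcile with it, and with footnote 16, the 15 June 2019 cut-off, the no-extension floor, the reason given for the February 2020 close, and the *may* and *will* wordings in the Synopsis, Section 2.1 and Section 3.
- Issue sites an end date for each child, computed from actual visit dates and the confirmed expiry.
- Restate the long-term safety exposure expected under the reconciled rule.

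The cost is a protocol wording change and a site memo. It should be done promptly, because most of the affected children are already in the extension and the rest are about to enter it.

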**Endpoints Derived from Evaluations:**

**Primary endpoints:** Language - Weighted child intentional communication score coded from a 22-minute structured task which is an examiner/child dyadic play session, including a structured play session and an unstructured play session.

**Key secondary endpoints:**

- Functional (all raw scores)
  - Mullen Scales of Early Learning (MSEL)
    - Developmental Quotient (DQ)
    - Expressive Language Subscore
  - Vineland Adaptive Behavior Scale – Version 3
    - Composite Score
    - Communication Subscore
  - Preschool Language Scale – 5th Edition (PLS-5)
    - Expressive Communication Score
  - McArthur Communicative Development Inventory
    - Number of spoken words
  - Clinical Global Impression-Improvement (CGI-I)
    - Overall Function

**Other Secondary endpoints:**

Safety measures including clinically significant laboratory values and adverse events will be tabulated for descriptive comparison between the placebo and active drug groups

- Functional

- Weighted Communication
  - Structured play score
  - Nonstructured play score
- Preschool Language Scale – 5th Edition (PLS-5)
  - Auditory Comprehension Subscore
  - Total Language Score
- Mullen Scales of Early Learning (MSEL)
  - Receptive Language Subscore
  - Visual Reception Subscore
  - Gross Motor Subscore
  - Fine Motor Subscore
- Vineland Adaptive Behavior Scale – Version 3
  - Communication
  - Daily Living Skills
  - Socialization
  - Motor
- Aberrant Behavior Checklist – Fragile X Validated Version (ABC-FX)
  - Irritability Subscore
  - Stereotyped Behavior Subscore
  - Abnormal Speech Subscore
  - Hyperactivity Subscore
  - Social Avoidance Subscore
  - Lethargy Subscore
- Visual Analog Scale (VAS) of Target Behavior (1, 2, & 3 sum)
- Visual Analog Scale (VAS) of Language
- Clinical Global Impression-Improvement (CGI-I)
  - Language
- Clinical Global Impression-Severity (CGI-S)
  - Overall Function
  - Language

A number of additional exploratory endpoints will be considered as well.

#### Sample Size and Population

100 subjects with FXS age 32 months to 6 years will be studied. In order to prevent age imbalance, randomization will be stratified by age with two strata, 3-4 years and 5-6 years.

#### **Inclusion Criteria**

1. Age 32 months to 6 years inclusive at Screening (visit 1).
2. Has a documented *FMR1* full mutation.  
\*\*Note\*\* Presence of mosaicism is allowed.
3. DQ<75 calculated from the Mullen Scales of Early Learning at time of screening.
4. Parent or legal guardian is available and able to communicate well with the investigator, comply with study requirements and provide written informed consent.  
\*\*Note\*\*The parent or legal guardian who will be signing consent form, should be the individual administering the language intervention.
5. English is the primary language spoken in the home and the subject's first language is English.
6. Meet criteria indicating evidence of intentional communication based on parent interview via a communication eligibility screening tool.  
\*\*Note\*\* On the Eligibility Screening Tool – Communication, the child must have at time of screening:

AFQ056 for Language Learning in Children with FXS

Version v15

Version date 02/03/2021

- a) Section 1: Answer of YES; the child uses at least 5 spoken words to label items on a daily basis.
- OR
- b) Section 2: At least 3 YES answers to items 1-10 if child does not have at least 5 spoken words.

7. Produces 3 or more intentional acts of communication on the structured portion of the Weighted Communication play sample at time of screening.

\*\*Note\*\* Subjects are permitted to use augmentative communication devices throughout the study if the device is the subject's primary form of communication and the device has been prescribed for the subject by an SLP.

8. Stable behavioral and other therapy regimen for 30 days prior to screening.

\*\*Note\*\* Patients will be allowed to continue their standard-of-care therapies throughout the trial but these will not be changed during the placebo lead-in or placebo-controlled portion of the trial, outside of standard changes occurring from school schedules.

9. Stable dosing of all concurrent psychotropic medications except stimulants for at least 60 days prior to screening. Due to the very short half-life of stimulants (specifically methylphenidate and amphetamine variants), a stable regimen of these medications is required for 2 weeks only.

\*\*Note\*\* Medications impacting GABA, glutamate and/or mGluR5 pathway receptors are exclusionary and not permitted during study participation. Additionally, stimulant regimens may include combinations of short- and long-acting forms and may be taken with different timing or dosing on different days of the week (e.g. Doses may be skipped on weekends or days off school and extra doses may be given some days for therapy sessions later in the day). The intent is to keep the doses and regimen being used at the time of screening consistent during the trial even if there is some variation in how the medication is taken on different days. Use of CBD oil or hemp based substances legal for sale over the internet are allowed provided that the dosing regimen has been consistent for at least 60 days prior to screening and will remain the same throughout the trial.

